Several modalities of treatment for amblyopia are available, yet occlusion treatment is the gold standard involving covering the good eye with a patch for a prescribed period of time ranging from 10 minutes daily to all waking hours **(Von Noorden and Campos, 2002; Stewart et al., 2005)**. However, its effectiveness decreases in older children and adults **(Pediatric Eye Disease Investigator Group, 2005)**

Disadvantages include prolonged treatment leading to poor compliance, patching related distress, relationship strain and stigma. In extreme cases, non-compliance with patching results in a costly hospital admission to supervise the patching treatment. In addition, wearing a patch eliminates any advantage of binocularity **(Dixon-Woods et al., 2006)**. Not to mention that not all patients respond to patching and of those who do, many have residual amblyopia after treatment is stopped regardless of compliance **(Hess et al., 2014)**. More importantly, binocular vision is not automatically restored once the vision in the amblyopic eye has been improved. In fact, once

the patch is removed after therapy, the amblyopic eye could be suppressed by the better seeing eye and can lose some of the gains achieved as a result of therapy. **(Birch, 2013)**

Another modality of treatment is atropine eye drops and optical penalization which are usually secondary treatments to failed patching but carrying the same disadvantages as the ordinary patching **(Foss et al., 2013)**

Advances in amblyopia treatment include dichoptic training, perceptual learning, and video gaming **(Tsirlin et al., 2015)**. These depend on the fact that the adult brain has been shown to be much more plastic than it was once believed to be and hence have the advantage of expanding the age of response in adults. **(Pizzorusso et al., 2002; He et al., 2006)**

Perceptual learning approaches have the advantage of being a dichoptic (binocular treatment) approach which is independent of age and type of amblyopia. **(Polat et al., 2004; Levi and Li, 2009)** Furthermore, it has been shown recently that therapy promotes binocular vision by strengthening stereopsis and reducing suppression **(Hess et al., 2010; Hess et al., 2011)**

A step further to conventional treatment is the use of a home-based approach allowing remote internet monitoring of treatment between office visits and hence better compliance. **(Hess et al., 2014)** In addition a video game version of the treatment is developed to make it more enjoyable for improving compliance. **(Foss et al., 2013)**. Moreover, dichoptic presentation can be achieved on the iPod device using a lenticular overlay screen. The advantage of using a lenticular overlay screen is that the luminance contrast is preserved **(Hess et al.; 2014)**

Aim of the work:

The aim of this work is to compare the gold standard occlusion therapy alone with dichoptic therapy

Patients and Methods:

Design:

The study will be a prospective experimental controlled study.

Patients of the study:

From the vicinity of the ophthalmology outpatient clinic of Ain Shams University Hospital, 100 patients of both sexes with amblyopia will be enrolled to this study. Informed consents will be obtained from adult patients and children's parents.

Patients will be assigned randomly into two groups:

Group A: 50 patients will receive the gold standard occlusion therapy

Group B: 50 patients will receive dichoptic treatment in the form of playing a video game (Lazy Eye Tetris games such as Lazy Eye Blocks ®) while wearing a red/green goggle.

Each group will be subdivided according to age:

1. From 4 to 7 years.
2. From above 7 to 12 years.
3. From above 12 to 30 years.

Hours of occlusion will be classified according to the degree of amblyopia:

- Mild to moderate amblyopia (Best corrected visual acuity (BCVA) < 0.2): 2-4 hours occlusion
- Severe (BCVA > 0.2): 4-6 hours occlusion

Hours of dichoptic treatment in group B will be classified according to the degree of amblyopia:

- Mild to moderate amblyopia (BCVA < 0.2): 2-4 hours of treatment
- Severe (BCVA > 0.2): 4-6 hours of treatment

Inclusion Criteria:

- Any degree of amblyopia
- Orthotropia in primary position.

Exclusion Criteria:

- Any ocular disease affecting vision
- Angle of deviation in primary position (Heterotropia)
- Adult patients and children's parents unwilling to enter or complete the study
- Ignorance of patients to use the video game

Methods

All patients will undergo the following:

- 1) Full medical and ophthalmic history
- 2) Examination:
 - A) External Appearance:
Anomalous Head Posture, globes (e.g., proptosis), lids (e.g. ptosis).
 - B) Refraction:
With and without cycloplegia.
 - C) Visual acuity:
With and without correction using Snellen acuity chart and preferential looking test for non-verbal patients.
 - D) Motility:
Ductions and versions (9 positions of gaze)
 - E) Angle of deviation if any
 - F) Fixation :
Fixation behavior (fixation preference) will be tested via base down 10 PD fixation preference test.
 - G) Quantitative Binocular vision assessment
 - H) Anterior segment examination.
 - I) Posterior segment examination using indirect ophthalmoscopy with a 20-D (diopter) lens through a dilated pupil.

All patients in Group A will receive the gold standard occlusion therapy. All patients in Group B will receive dichoptic treatment

Treatment assessment:

All patients will be followed up in the following schedule: after 1 month, after 2 months and after 6 months with regards to visual acuity. Patients who fail to complete the full time of the follow up period will be excluded from the study.

References:

- 2) Aldebasi YH. Prevalence of amblyopia in primary school children in Qassim province, Kingdom of Saudi Arabia. *Middle East Afr J Ophthalmol.* 2015;**22**(1):86-91
- 3) American Academy of Ophthalmology Basic and Clinical Science Course Subcommittee. Basic and Clinical Science Course. Pediatric Ophthalmology and Strabismus: Section 6. San Francisco, CA: American Academy of Ophthalmology. 2012.pp.61.
- 7) Birch EE. Amblyopia and binocular vision. *Progress in retinal and eye research* 2013;**33**:67-84

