A Comparative Study between Dissociative Treatment and Binocular Interactive Treatment in Amblyopia

Thesis

Submitted to Faculty of Medicine – Ain Shams University
In Partial Fulfillment of the Requirements of Doctorate Degree in Ophthalmology
By

[name]

M.B,B.C.h (2009) , M.Sc (2014) ,

Faculty of medicine - Ain Shams University

Under supervision of

[name]. [name]

Professor of Ophthalmology
Faculty of medicine – Ain Shams University

[name]. [name]

Professor of Ophthalmology
Faculty of medicine – Ain Shams University

[name] [name]

Lecturer of Ophthalmology
Faculty of medicine – Ain Shams University

[name] [name]

Lecturer of Ophthalmology
Faculty of medicine – Ain Shams University

Faculty of medicine
Ain Shams University
Cairo – Egypt
2017

STATISTICAL ANALYSIS PLAN

Using the SPSS (or the Minitab or Mega Stat) statistical software, the data will be examined using standard summary statistics which will include, where appropriate, 95% confidence intervals.

A one-way analysis of variance (ANOVA) will be performed on the visual acuity data to determine whether there appeared to be an effect of measurement time on visual acuity, and pairwise comparisons of mean will then be performed, examining the changes from baseline to 1 month, 3 months and 6 months after treatment start.

An improvement of ≥ 0.125 LogMAR units will be considered clinically significant. In addition, the proportion of change will be calculated at 1 month, 3 months and 6 months follow up as follows (using the formula described by Stewart et al)

$$\text{Proportion of change} = \frac{VA_{as} - VA_{ae}}{VA_{as} - VA_{fe}}$$

Where VA_{as} is the vision of amblyopic eye at baseline, VA_{ae} is the vision of amblyopic eye at the end of the treatment (i.e. 6months) and VA_{fe} is the vision of the non-amblyopic eye at the end of the treatment.

Also percentage of compliance with treatment in each group will be measured as a secondary outcome measure.

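### No stratification by severity is stated and the analysis adjusts for neither severity nor baseline acuity, which costs precision and leaves a chance imbalance uncorrected

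*Protocol*

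**What the plan says.** Protocol, Patients of the study: "100 patients of both sexes with amblyopia will be enrolled to this study", and "Patients will be assigned randomly into two groups". The arms are equal: "Group A: 50 patients will receive the gold standard occlusion therapy" and "Group B: 50 patients will receive dichoptic treatment in the form of playing a video game". No stratification factor, blocking or method of generating the list is given. Age is the only subdivision named ("Each group will be subdivided according to age"), and it is not described as a randomisation stratum.

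The same section then uses a two-level severity band to set hours in each arm: "Hours of occlusion will be classified according to the degree of amblyopia", and "Hours of dichoptic treatment in group B will be classified according to the degree of amblyopia". The bands and hour ranges (2-4 and 4-6) are identical in the two arms. The inclusion criteria admit every degree of amblyopia, so the severity mix is left open.

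SAP, second paragraph: "A one-way analysis of variance (ANOVA) will be performed on the visual acuity data to determine whether there appeared to be an effect of measurement". The factor tested is when acuity was measured, and pairwise comparisons of change from baseline follow. The third paragraph sets 0.125 logMAR as the clinically significant improvement and adds a proportion of change scaled to each patient's own deficit. The SAP contains no treatment term, severity term or baseline-acuity term.

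**The concern.** The sponsor treats severity as important enough to set treatment intensity. It is known before allocation, because acuity is part of the entry examination (Protocol, Methods, item C), and it plausibly predicts how much acuity changes. Such a factor is normally balanced by the randomisation, adjusted for in the analysis, or both. Here neither is stated.

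Two things are at stake. Variation in outcome that baseline acuity could explain stays in the error term, so the comparison is less precise than 100 patients allow. And if this one randomisation happens to be uneven on severity, nothing planned would correct the difference between arms.

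**Working it through.** **Inputs from the documents:** 100 patients, 50 per arm; two severity bands; threshold 0.125 logMAR.

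**Assumed, because the documents give no figure:** severe patients K = 20 to 50 of 100; difference g in mean acuity change between bands = 0.10 or 0.20 logMAR; within-band SD 0.20 logMAR.

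The plan gives no figure for balance or power that could be reproduced.

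**1. How uneven can the arms be?** With arms fixed at 50, the number X of severe patients in Group A is hypergeometric (100, K, 50). The gap in severe share is (2X - K)/50, with SD (2/50) x sqrt[50 x (K/100) x (1 - K/100) x 50/99]. For K = 50 this is 0.04 x sqrt(6.313) = 0.04 x 2.513 = 10.1 points. A 12-point gap is 6 patients; a 20-point gap is 10.

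| K severe of 100 | SD of gap (points) | P(gap of 12 points or more) | P(gap of 20 points or more) |
|---|---|---|---|
| 20 | 8.0 | 0.211 | 0.023 |
| 30 | 9.2 | 0.275 | 0.049 |
| 40 | 9.8 | 0.307 | 0.066 |
| 50 | 10.1 | 0.317 | 0.071 |

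The figures are the same for 100 - K, so 50 to 80 severe patients give the same range. A gap of 14 or more patients has a chance below 1% throughout.

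**2. What does a gap do to the crude difference?** Shift = gap x g.

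- 12 points: 0.12 x 0.10 = 0.012 to 0.12 x 0.20 = 0.024 logMAR.
- 20 points: 0.20 x 0.10 = 0.02 to 0.20 x 0.20 = 0.04 logMAR, which is 16% to 32% of 0.125.

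**3. What is lost on average?** With K = 50, the outcome variance without adjustment is 0.20² + g² x 0.5 x 0.5.

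- g = 0.10: 0.0400 + 0.0025 = 0.0425; SE = sqrt(0.0425 x 2/50) = 0.041.
- g = 0.20: 0.0400 + 0.0100 = 0.0500; SE = sqrt(0.0500 x 2/50) = 0.045.
- Adjusted for band: SE about sqrt(0.0400 x 2/50) = 0.040.

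The variance ratios are 0.0425/0.0400 = 1.06 and 0.0500/0.0400 = 1.25.

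**4. Simulation of the test** (20,000 runs per setting, K = 50, SD 0.20):

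| | Unadjusted | Adjusted for band |
|---|---|---|
| Type I error, all randomisations (either g) | about 0.05 | about 0.05 |
| Type I error when the gap is 10 or more patients, g = 0.10 | 0.08 | about 0.05 |
| Type I error when the gap is 10 or more patients, g = 0.20 | 0.14 | about 0.05 |
| Power for a true effect of 0.125, g = 0.10 | 0.85 | 0.87 |
| Power for a true effect of 0.125, g = 0.20 | 0.79 | 0.87 |

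The mean of the unadjusted estimate equals the true effect to within simulation error.

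**5. Within age bands.** The documents give no age-band sizes. For 33 patients (17 v 16, 16 severe) a gap of 20 points or more has a chance of 0.303; for 34 (17 v 17, 17 severe) it is 0.169. The figure depends heavily on the exact counts, and no between-arm test within age bands is planned, so little should rest on it.

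**The case against.** The strongest reply is that randomisation already does its job. Chance imbalance is not systematic confounding: step 4 shows no bias and a type I error of about 0.05 without any adjustment. That stands. Stratification and adjustment buy precision and protect against an unlucky draw; they are not conditions for validity.

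A reader might infer more than the documents support in three ways.

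- *That the randomisation disregards severity.* The Protocol does not describe the method at all. It can be said only that no stratification is stated.
- *That hours are a second confounder.* Hours follow severity by one rule with the same ranges in both arms, so prescribed hours belong to each regimen. Any imbalance in hours is the severity imbalance seen again.
- *That one arm is likely to hold many more severe patients.* A gap of 10 or more has a 2-7% chance. The more common 12-point gap moves the crude difference by only 0.012-0.024 logMAR.

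Three further replies carry weight. The SAP's change scores and proportion of change deal in part with differing room to improve, though they do not replace a baseline term in a between-arm model. The SAP specifies no Group A v Group B test, so there is at present no model to carry such a term; that gap is the larger defect, and filling it with a baseline-adjusted model would largely settle this point. Finally, the only prognostic remark in the Protocol's introduction concerns age, so the prognostic role of severity is a reasonable assumption and not something the documents state.

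**Conclusion.** The point holds as one of efficiency and robustness, not of bias. A factor that is known at entry and sets hours is neither balanced by any stated procedure nor adjusted for. The chance of a 12-point gap in severe share is about 21-32% and of a 20-point gap about 2-7%; the latter would shift the crude difference by 0.02-0.04 logMAR against 0.125. Adjustment raises power from 0.85 to 0.87 or from 0.79 to 0.87.

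These sizes rest on an assumed 20-50 severe patients of 100, a 0.10-0.20 logMAR difference in mean change between bands and, for power, a within-band SD of 0.20 logMAR. That no stratification or adjustment is stated does not depend on these assumptions.

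**What to change.** 1. In the SAP, specify the Group A v Group B comparison of 6-month amblyopic-eye acuity as an analysis of covariance with treatment and baseline amblyopic-eye acuity. Baseline acuity is already measured, so this costs one or two sentences and can be done whether or not enrolment has begun.
2. If enrolment has not started, also stratify the randomisation list by severity band with permuted blocks, and include the band in the model. This would hold the imbalance to a few patients, depending on block size. If enrolment has started, keep the list and rely on step 1.
3. Before the band is used as a stratum or model term, reconcile the 0.2 cut-off. Its scale is not stated: the Protocol examines acuity on a Snellen chart and the SAP works in logMAR. Values above 0.2 mean worse vision in logMAR but better vision in decimal notation. A value of exactly 0.2 falls in neither band.

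The cost of step 2 is one list per band and the need to determine the band before allocation, which the entry examination allows. No patients or visits are added.

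### The plan specifies no stratification of the randomisation by age, so the age mix of the arms and the arm sizes within the three age bands are left to chance

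*Protocol*

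**What the plan says.** The Protocol, under Patients of the study, plans that "100 patients of both sexes with amblyopia will be enrolled to this study". It continues: "Patients will be assigned randomly into two groups", with 50 patients on occlusion in Group A and 50 on the dichoptic video game in Group B. After defining both groups it adds: "Each group will be subdivided according to age". The bands are "From 4 to 7 years", "From above 7 to 12 years", and above 12 to 30 years. No band has a target number.

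Neither the Protocol nor the SAP mentions stratification, blocking or minimisation, or says how the random sequence is generated.

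The Protocol's background, before the Aim of the work, says of occlusion: "However, its effectiveness decreases in older children and adults". The same background describes the dichoptic, perceptual-learning type of treatment as not depending on age.

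The only model named in the SAP is a one-way analysis of variance for measurement time. The SAP has no age term and no analysis by age band.

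**The concern.** Age is recorded before allocation, the protocol has already chosen three bands, and its own background treats age as affecting response to the control treatment. These are the usual grounds for stratifying. As written, nothing ties the allocation to the bands.

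Two things could follow. The arms could differ in their share of young children, which would move the pooled arm difference for reasons unrelated to treatment. Any comparison within a band could also rest on unequal arms. Nothing in the SAP would correct for either. Balance at allocation cannot be restored later; it can only be adjusted for.

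**Working it through.** The plan gives no figure on this point to reproduce. Its 50 per arm comes without alpha, power, standard deviation or target difference. The check is therefore how much age imbalance chance produces.

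**Inputs.** From the Protocol: 100 patients, 50 per arm, three age bands. Assumed, because the documents do not give them: band sizes of 34/33/33, 50/30/20 or 60/25/15 (youngest first), and a difference in mean gain of 0.10 to 0.20 LogMAR between the youngest and the older patients.

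**1. Arm sizes within one band.** With 50 of 100 allocated to Group A, the number from a band of *m* patients who fall in Group A is hypergeometric, with mean *m*/2 and SD = √[*m* × ¼ × (100 − *m*)/99].
- *m* = 33: SD = √(33 × 0.25 × 67/99) = 2.36; 95% range 12 to 21.
- *m* = 15: SD = √(15 × 0.25 × 85/99) = 1.79; 95% range 4 to 11.

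**2. All three bands together** (multivariate hypergeometric simulation for the second column, exact calculation for the last two).

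| Assumed bands | At least one band split 2:1 or worse | Share of 4-7-year-olds differs by ≥16 points | Median gap in that share |
|---|---|---|---|
| 34/33/33 | 7% | 14% | 8 points |
| 50/30/20 | 12% | 16% | 8 points |
| 60/25/15 | 31% | 15% | 8 points |

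A 16-point gap is a difference of 8 patients (8/50). The 31% comes mainly from the assumed band of 15, which alone reaches 2:1 or worse with a chance of 26%.

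**3. Precision lost within a band.** The standard error is proportional to √(1/*n*₁ + 1/*n*₂).
- Band of 33: 0.348 at 16:17; 0.362 at 12:21 (+4%); 0.369 at 11:22 (+6%).
- Band of 15: 0.518 at 7:8; 0.584 at 4:11 (+13%).

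**4. Shift in the pooled arm difference.**
- Gradient in both arms: shift = gap × gradient. For 16 points, 0.16 × 0.10 = 0.016 and 0.16 × 0.20 = 0.032 LogMAR.
- Gradient under occlusion only: just Group A's departure from the pooled age mix counts. With equal arms this is half the gap: 0.08 × 0.10 = 0.008 and 0.08 × 0.20 = 0.016 LogMAR.
- At the median gap of 8 points these halve again, to 0.008-0.016 and 0.004-0.008.

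**5. What adjustment alone recovers.** With age band in the model and no stratification, the information on the arm difference is Σ *n*₁*n*₂/(*n*₁ + *n*₂) over bands; perfect balance gives Σ *m*/4 = 25. In simulation the standard error is on average about 1% larger than under perfect balance, and about 4% larger at the 97.5th percentile, for all three mixes.

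**6. After stratifying.** With blocks of 4, for example, the arms in a band cannot differ by more than 2 patients at allocation.

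**The case against.** The strongest reply is that unstratified 1:1 randomisation of 100 patients is an accepted choice. Chance imbalance is not bias, and ordinary confidence intervals already allow for it. Uneven arms within a band cost little; what limits a band is its small total, which stratification does not change. An age factor in the analysis recovers nearly all the precision without touching the allocation. Stratification also cannot protect the balance against the later exclusion of non-completers, which the Protocol plans under Treatment assessment. All of this stands, and it makes the point minor. It does not remove it: no age factor is planned at present, and both changes cost almost nothing.

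Three stronger readings are tempting, and the documents do not support them.

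- A reader might infer that patients are definitely randomised as a single pool and sorted by age only afterwards. That rests on the order of the sentences. The procedure is not described, so an unreported stratified scheme cannot be excluded; what can be said is that none is specified.
- A reader might conclude that the band comparisons would be badly compromised by uneven arms. Step 3 shows a loss of 4-6% in standard error for a band of 33, and 13% for an unfavourable split of a band of 15.
- A reader might set the shift of 0.016-0.032 against the SAP's 0.125 LogMAR. The SAP introduces that figure as a clinically significant improvement, alongside changes from baseline, and does not state it as a between-arm margin. The shift also assumes an equal age gradient in both arms, whereas the background presents the dichoptic approach as unaffected by age.

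**Conclusion.** The point holds as a cheap improvement of minor severity. No stratification by age is specified, although the protocol's own background makes age relevant to the control treatment. What is left to chance is the age mix of the arms and, less importantly, the arm sizes within bands.

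The main consequence is avoidable noise in the arm comparison. Even at the less usual 16-point gap, the shift is 0.008-0.032 LogMAR across the two gradient assumptions. The probabilities rest on assumed band sizes, and the shifts on an assumed gradient; the documents give neither. The validity of the randomised comparison is not in question.

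**What to change.** In the Protocol, under Patients of the study, state that patients are randomised 1:1 within each of the three age bands, from separate lists in permuted blocks of randomly varying size. In the SAP, include age band as a factor in the between-arm comparison. The age factor brings most of the gain; stratification adds balance within the bands.

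If enrolment has begun, stratify the remaining patients and keep the age factor for everyone.

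The cost is three lists in place of one, with no extra patients, visits or data. Incomplete last blocks mean that the arms may not come out at exactly 50:50.

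### The protocol divides each arm into three age bands and its background implies that the arm difference may vary with age, but the SAP has no between-arm acuity model and makes no use of age band or baseline acuity.

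*Protocol*

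**What the plan says.** **Design.** In the protocol's Patients of the study section, "100 patients of both sexes with amblyopia will be enrolled to this study", randomly assigned 50 to occlusion and 50 to dichoptic treatment. It then says "Each group will be subdivided according to age" and lists three bands: 4 to 7 years, above 7 to 12 years, and the widest, "From above 12 to 30 years". It gives no number per band, no purpose for the bands, and no statement that assignment is made within them.

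**Background.** The protocol's introductory text says of occlusion that "its effectiveness decreases in older children and adults". It describes perceptual learning, which it classes as dichoptic, as an "approach which is independent of age and type of amblyopia". It also says that the newer treatments widen the age range of response in adults.

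**Aim.** The one stated aim is to compare occlusion with dichoptic therapy. Age is not mentioned in it.

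**Analysis.** The SAP plans summary statistics, a one-way ANOVA to "determine whether there appeared to be an effect of measurement time on visual acuity", pairwise changes from baseline, a threshold of 0.125 logMAR for a clinically significant improvement, a proportion of change, and compliance in each group. Compliance is the only item reported by treatment group. Age, age band and the severity class that sets treatment hours do not appear.

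**The concern.** If one treatment's effect falls with age and the other's does not, the difference between them changes with age. The protocol's background makes both statements and its design sets up age bands, yet the SAP gives the bands no role. Two things are at stake.

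- **Interpretation.** An arm difference taken over all ages from 4 to 30 would be an average whose value depends on how many patients of each age happen to be recruited. Any age-band result reported later would have been chosen without a prior plan.
- **Precision.** Age and baseline acuity are recorded for every patient. If they predict change in acuity, leaving them out makes the arm comparison less precise than the same data allow.

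Both depend on a more basic gap. The SAP's ANOVA has measurement time as its factor, so there is no between-arm acuity comparison for age to enter.

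**Working it through.** The documents give no alpha, power, between-arm effect or SD, so there is no planned figure to reproduce. Everything below is illustration.

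**Inputs from the documents:** 50 patients per arm; three age bands; 0.125 logMAR, which the SAP defines as an important improvement and which is borrowed here as a difference.

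**Inputs assumed:** equal bands, so 50/3 ≈ 17 per arm per band; SD of change 0.15 to 0.20 logMAR; two-sided alpha 0.05.

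**1. Dependence on age mix.** Pooled difference = sum of (band share × band difference). Assume that dichoptic minus occlusion gain is 0, 0.0625 and 0.125 logMAR from youngest to oldest band.
- Mix 60/30/10%: 0.6×0 + 0.3×0.0625 + 0.1×0.125 = 0.031
- Equal mix: (0 + 0.0625 + 0.125)/3 = 0.0625
- Mix 10/30/60%: 0.1×0 + 0.3×0.0625 + 0.6×0.125 = 0.094

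The same true effects give a pooled value from 0.031 to 0.094, a span of about 0.063.

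**2. Precision from covariates.** The SE with covariates, relative to that without, is √(1−R²). The equivalent gain in sample size is 1/(1−R²) − 1. R² is assumed.

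| R² | SE ratio | SE reduction | Equivalent extra patients |
|---|---|---|---|
| 0.10 | 0.95 | 5% | 11% |
| 0.20 | 0.89 | 11% | 25% |
| 0.30 | 0.84 | 16% | 43% |

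**3. Precision within a band.** 95% half-width = t × SD × √(2/n).
- Within a band (n = 17 per arm, t on 32 df = 2.037): 2.037×0.15×√(2/17) = 0.105; with SD 0.20, 0.140
- All ages (n = 50 per arm, t on 98 df = 1.984): 1.984×0.15×√(2/50) = 0.060; with SD 0.20, 0.079

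**4. Power for a difference in arm effect between two bands.** SE = SD × √(4/17). Power ≈ Φ(0.125/SE − 1.96).
- SD 0.15: SE = 0.073; Φ(1.718 − 1.96) = 0.40
- SD 0.20: SE = 0.097; Φ(1.288 − 1.96) = 0.25

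The difference detectable with 80% power is (1.96 + 0.84) × SE, or 0.20 to 0.27 logMAR. The protocol's Treatment assessment section excludes patients who do not complete follow-up, so actual bands may be smaller and precision worse.

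**The case against.** The strongest reply is that the trial never set out to study age. Its only aim is the comparison of treatments. The interaction comes from joining separate background sentences, and the one about age independence concerns perceptual learning approaches, which the same text also lists as a separate item from dichoptic training and video gaming. This stands. The background implies that the effect may vary with age, but it states no such hypothesis. A reader might infer that the trial fails to answer an age question it was built to answer; the documents do not support that.

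Second, a pooled estimate is not wrong. It is a valid average for the patients recruited, and the shift in step 1 (about 0.063) is no larger than the uncertainty of the pooled result itself (about 0.06 to 0.08). A reversal of sign can be produced: assumed differences of −0.05, 0 and +0.10 give −0.005 with a 50/30/20% mix and +0.040 with 20/30/50%. But nothing in the documents says that occlusion is superior in young children. This stands too.

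Third, the R² values have no source, and the documents do not say that baseline severity predicts change in acuity. So the precision gain is possible but not established.

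Fourth, unstratified assignment is not an error. With 34/33/33 patients per band and 50:50 assignment, the chance that some band differs between arms by 5 or more patients is 63%. Such imbalance is not bias in expectation, and adjustment for age band would deal with most of it.

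Finally, the trial is too small to settle the age question under any analysis. That is true, and it is why the band-specific results should be labelled exploratory. It does not explain why age bands are declared and then given no use.

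**Conclusion.** The point holds as an inexpensive improvement to the analysis. Three facts need no assumption: each arm is divided into age bands, the background implies that the arm difference may change with age, and the SAP has neither a between-arm acuity model nor any use of age band or baseline acuity.

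Its size does rest on assumptions. Over the age mixes shown, a pooled difference could run from 0.031 to 0.094 logMAR if the arm difference rose from 0 to 0.125 across the bands. Adjustment could cut the standard error by 5% to 16% if the covariates explained 10% to 30% of the variance. Neither premise comes from the documents.

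A reader might conclude that the SAP commits to one misleading pooled result. It does not, because it specifies no arm comparison for acuity at all, pooled or by band. That is the first thing to put right, and age belongs in the same model.

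**What to change.** 1. Specify a between-arm model for change in logMAR acuity from baseline, at a named visit, with treatment arm, baseline acuity and age band as covariates. Measured baseline acuity is a better covariate than the severity class, whose cut-offs state no acuity scale and leave a value of exactly 0.2 unclassified.
2. Add an arm-by-age-band term in a further analysis. Report the arm difference with its 95% confidence interval in each band, labelled exploratory.
3. State the limits in the SAP: with about 17 per arm per band, expect half-widths of about 0.10 to 0.14 logMAR and interaction power of about 25% to 40% under the assumptions above, and less if patients are lost. The 100 patients should not be presented as powered for an age interaction.
4. Optionally, assign patients not yet assigned from separate block lists for the three bands.

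**Cost:** a few lines in the SAP and, if item 4 is taken up, three assignment lists in place of one. No new data are needed, since age and acuity are already recorded. The price is wide within-band intervals, which must be reported as such.
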